7.4.7.2 Reporting Serious Adverse Events

All SAEs, including any fatal or life-threatening event, must be reported within 24 hours from the time the Investigator is made aware of the event. If the Investigator does not have all information regarding an SAE, he/she will not wait to receive additional information before recording the event in the data system and completing as much information known at the time of the submission. The reporting timeframes for any SAE occurring during the study are summarized in [Table 3](#).

All SAEs are to be reported as follows:

- Site completes the SAE Report Form (initial and/or follow-up) and faxes the completed form to UBC Safety at [name].
- UBC Safety will review all information provided and contact the Investigator for additional information, as necessary. The DSMB will receive regular safety updates from the Sponsor. The Sponsor or designee is responsible for notifying the DSMB of all SAEs as described in [Table 3](#).
- Per ICH E2A and 21 CFR 312, regulatory agencies will be notified by the Sponsor by telephone or fax of any unexpected, SAR potentially associated with treatment as soon as possible, but in no event later than 15 calendar days after the Sponsor's initial receipt of the information; fatal or life-threatening unexpected SAEs associated with treatment will be reported to regulators within 7 calendar days. Follow-up information will be provided as required.

Table 3. Serious Adverse Event Reporting Requirements

| Serious Adverse Event Reporting Requirements | | | |
|--|---|--|----------|
| | Initial Reports | Follow-Up Reports | |
| Type of SAE | Serious, Unexpected, Reasonable Possibility Causality | All Other SAEs | Any SAE |
| Reporting Timeframes (Site to Sponsor) | 24 hours | 24 hours | 72 hours |
| Reporting Timeframes (Sponsor to DSMB) | Notification will occur in parallel with applicable Regulatory Agencies | Aggregate reporting at time of DSMB meetings | |

All AEs and SAEs documented at a previous visit/contact that are designated as ongoing will be reviewed at subsequent visits/contacts.

All AEs (including SAEs) will be followed until resolution, until no further changes in the event are expected (i.e. the point at which a subject experiencing an adverse event is treated successfully and stabilized even though they may continue to experience sequelae) as confirmed by the Investigator, until the subject is lost to follow-up, or until the subject's 12 Month Visit. Subjects will be contacted by phone annually through year 5 post-infusion to assess for MACE as described in Protocol Section 7.3.7. If a subject dies during participation in the study or during a recognized follow-up period, the Medical Monitor will be provided with a copy of any post-mortem findings, including histopathology.

New or updated information will be recorded by modifying the AE forms in the electronic data system.

The Investigator will promptly report all SAEs within the timeframes specified in [Table 3](#). The Investigator will comply with the applicable local regulatory requirements related to reporting of SAEs to his or her Institutional Review Board (IRB) or Independent Ethics Committee (IEC).

This protocol is being filed under an investigational study with the appropriate regulatory agencies. A given SAR may qualify for an Expedited Safety Report (ESR) if the SAE is serious, unexpected, and has a reasonable possibility that the drug caused the event. In this case, all Investigators participating in the study will receive the ESR. The purpose of the ESR is to fulfill specific regulatory and Good Clinical Practice (GCP) requirements regarding the product under investigation.

7.4.7.3 *Sponsor Monitoring of Adverse Events*

This study will be overseen by two distinct data safety monitoring boards (DSMBs): The National Heart, Lung and Blood Institute (NHLBI) DSMB will review the 14 subjects in the Safety Cohort and an independent DSMB appointed by the Sponsor will review the Randomized Cohort and will have access to all Safety Cohort reports and NHLBI DSMB recommendations.

The following list summarizes the Sponsor's role in monitoring AE/SAEs:

- All SAEs will be reviewed on a monthly basis by the Sponsor's Medical Monitor or designee.
- The Sponsor is responsible for notifying the DSMBs of all SAEs, and of any concerns regarding the frequency or type of SAE(s) on a study or treatment cohort.
- The Sponsor will prepare summary reports of all AEs/SAEs approximately every 6 months for the NHLBI-sponsored DSMB (Safety Cohort subjects) and for the study-sponsored DSMB (all subjects enrolled).

7.4.7.4 *DSMB Monitoring of Adverse Events*

This section generally applies to both the NHLBI and independent DSMB, but the NHLBI DSMB will review materials from only the fourteen subjects enrolled in the Safety Cohort. The following list summarizes roles of the DSMBs in monitoring AE/SAEs

- The DSMBs will review all SAEs. The Sponsor will report serious, unexpected and potentially related SAEs to the DSMB in parallel with reporting to applicable Regulatory Agencies. The DSMB chair (or designee) will be requested to acknowledge receipt of SAEs within 72 hours of notification.
- Approximately every six months the DSMBs will be provided with a summary (aggregate) of all AEs and SAEs, regardless of attribution, and additional safety and outcomes data as part of their scheduled interim reviews. In addition to AE and SAE review, specific safety and outcomes data will be identified for review by the DSMBs.
- The DSMB Chair (or designee, e.g., NHLBI Project Officer) is responsible for reviewing the SAE materials to determine if the documents are complete. If there are any concerns regarding the type or frequency of the event, the DSMB Chair may request additional information from the Sponsor. The DSMB Chair will determine whether additional DSMB review is required and make recommendations to the Sponsor regarding continuation of the study.

7.4.8 Post-Study Adverse Events and Serious Adverse Events

The Investigator should notify the Medical Monitor of any death or SAE occurring at any time after a subject has completed or terminated a clinical trial, when such death or SAE may reasonably be related to the study therapy used in this investigational trial. Investigators are not obligated to actively seek AEs from former study participants.

7.5 Removal of Subjects from the Trial or Study Drug

The Investigator may withdraw a subject from participation in the study for any of the following

reasons:

- A protocol violation occurs,
- An intolerable adverse event occurs, that affects continuation of subject's participation in the study,
- The Sponsor or Investigator terminates the study, or
- The subject requests to be discontinued from the study.

Subjects who become pregnant during the study following the study infusion will be followed during the pregnancy and through birth of the newborn. Subjects who become pregnant prior to receiving the study infusion will be withdrawn from the study.

7.6 Other Study Procedures

For subjects who so consent, serum for clinical research into biomarkers will be collected at every scheduled visit and sent to the Sponsor for analysis.

7.7 Appropriateness of Measurements

Usual safety measurements will be obtained and summarized per standard reporting. In addition, more in depth evaluation of safety data as it relates to cardiac events will more fully elucidate the safety profile for CAP-1002. Events to be assessed in greater detail include all MACE events, myocarditis, change in TIMI flow to ≤ 1 following infusion, troponin and CK- MB elevations, ventricular tachycardia events, and increases in anti-HLA antibodies as indicative of sensitization to CAP-1002 donor antigens.

With respect to efficacy, the perfect surrogate remains elusive in terms of cardiac disease given the complexity of the heart failure syndrome. Data suggest that markers of the biological process of left ventricular hypertrophy and enlargement (remodeling) and the factors that contribute to this process may be viewed as surrogates for progression of the disease as may functional measures and neurohormones ([Anand, Florea, & Fisher, 2002](#)). More specifically, it has been shown that the validity for infarct size as measured by MRI under a common imaging protocol is relatively high when used as a surrogate endpoint for clinical outcomes ([Desch et al., 2011](#)). In addition, the ability of infarct size to predict clinical endpoints has been demonstrated in epidemiological studies ([Larose et al., 2010](#); [Wu et al., 2008](#)).

In this trial, the primary efficacy endpoint is change in infarct size (relative to LV size). Infarct size represents the extent of myocardial injury sustained after an MI. Infarct size is likely the single most important defining factor of the remodeling process, leading to change in function, volume and geometry of the LV. Use of a common imaging protocol in the study ensures high measurement reliability for infarct size. Infarct size may prove in this study, as in prior studies, to be a reasonable MRI surrogate endpoint that correlates with long term subject outcome.

7.8 Payment to Subjects

Subjects will be paid \$100, as applicable in clinical site budgets, for the Screening, Infusion, Month 6, and Month 12 visits. Subjects will be paid \$50 for all other visits (Week 2, and Months

1, 2 and 3). These disbursements are intended to cover the costs required to complete these study visits. Necessary travel expenses (reasonable hotel, meals and fuel) and parking expenses may be reimbursed, depending on the individual circumstances. Study staff will contact the Sponsor to request reimbursement on a case by case basis.

The total amount the subject will receive if they complete the whole study is \$550. Safety Cohort subjects will receive up to \$650 for extra testing and visits conducted in the Phase I portion of the study. Subjects will only be paid for those visits and procedures that they complete.

7.9 Early Termination Procedures

Every reasonable effort will be made to retain subjects in the study. In the event that a subject must be withdrawn from the study early, study personnel should attempt to obtain testing and data required for the 12 Month Visit (see [Section 7.3.6](#)) as well as the reason for withdrawal, if known. If the subject permits, he or she should be contacted by study personnel at the time of their usual study visits (and annually through 5 years post-infusion), as described in the protocol.

Follow-up of adverse events that result in discontinuing the subject from the study will continue until resolution, until the event has stabilized as confirmed by the Investigator, or until the event has been determined to be caused by an agent other than the study drug.

All consenting subjects, including those who discontinued early from the study, will be contacted by phone annually on the anniversary of their infusion through year 5 post-infusion to assess for MACE, defined as the composite incidence of death, non- fatal recurrent MI, hospitalization for heart failure, emergency room treatment for heart failure (NT-proBNP >450 pg/mL or BNP>100 pg/ml, with treatment including intravenous diuretic administration), left ventricular assist device (LVAD) placement or heart transplant.

A subject can be considered “lost to follow-up” if he or she misses a visit and study personnel are unable to contact him or her in a timely manner with a minimum of three documented phone calls. If contact with the subject is not accomplished, study personnel should follow-up with certified mail in the following manner:

1. Mail a certified letter with return receipt requesting contact and expressing concern for the subject’s well-being.
2. If the subject does not respond within seven days, mail another certified letter with return receipt stating that the subject’s participation in the study has been terminated.
3. If a signed mailing receipt for the second letter is returned, record the termination date as the date the subject signed it. Otherwise, record the termination date as the date the second letter was mailed.

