## 7.6 Study Period and Time Point Definitions

The following study periods and time points are defined:

Screening Period: the 4-week time period before IP infusion.

Baseline: the last observation of a given parameter before IP infusion of a given subject.

Day 0: the day of planned IP infusion of a given subject.

(Nominal Visit) Analysis Time Point: analysis based on data collected at the *(nominal visit)* time point, where nominal visits are as shown in the table below.

EOS, Subject Level: subject-level EOS is reached after completion of the Month 12 visit or study or discontinuation for any reason.

EOS, Study-Level: study-level EOS is reached when all randomized subjects have either completed the Month 12 visit or have discontinued from the study for any reason.

Long-Term Follow-Up (LTFUP) Period, Subject-Level: the LTFUP period begins after completion of the Month 12 visit and continues until 4 more annual visits have been completed.

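### Protocol 7.9 permits a subject to be told that participation is over after one missed visit, well before the Month 6 and Month 12 MRIs, and gives no route back

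*Protocol*

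**What the plan says.** Protocol 7.9 opens with a commitment: "Every reasonable effort will be made to retain subjects in the study". When a subject is withdrawn early, "study personnel should attempt to obtain testing and data required for the 12 Month Visit". If the subject permits, staff should also make contact at the usual visit times and yearly to year 5. Consenting subjects, including those who left early, are phoned yearly about MACE (also Protocol 7.3.7).

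The same section then lets a site class a subject as lost "if he or she misses a visit and study personnel are unable to contact him or her in a timely manner". At least three calls must be on record. The section sets no spacing of calls and no calling period, and it does not define what is timely. The site mails a certified letter and waits seven days. Without a reply, a second certified letter tells the subject that "participation in the study has been terminated". If the receipt for that second letter comes back signed, the signature date is the termination date. Otherwise the site is to "record the termination date as the date the second letter was mailed".

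In the SAP, section 7.6 states that "subject-level EOS is reached after completion of the Month 12 visit or study or discontinuation for any reason". Section 8.9 runs follow-up to the latest of several dates, the EOS date among them. Section 10.2 uses days of follow-up as the offset for the secondary safety event rates.

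**The concern.** Treatment is one infusion on Day 0. A subject who misses an interim visit can therefore still give a valid Month 6 or Month 12 MRI and valid safety information. A rule that can end participation after a single missed visit may turn a minor gap into a missing primary endpoint. It applies equally to Week 2, Month 1 and Month 3, which have no MRI. It also applies to a subject who signs for the second letter and so has just been shown to be alive and reachable by post.

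What is at stake is missing data that need not be missing and may be related to outcome. SAP section 9 itself allows that subjects who do worse may be likelier to miss assessments. There is a smaller cost on the safety side: a termination date set by a mailing can count as follow-up time during which nobody observed the subject.

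**Working it through.** **The plan's own attrition figure.** Protocol 3.1 plans 103 randomized with 10% non-completion: 103 × (1 − 0.10) = 92.7, or 93 completers. This reproduces. It is the only stated figure that bears on loss to follow-up, and it does not separate losses made by this rule from any others.

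**Timing.** Inputs are the visit windows in Protocol 7.3 and the seven-day wait in 7.9. I assume that the three calls and the first letter are all done on the day the missed visit's window closes, so second letter = window close + 7. This is the fastest sequence under that assumption.

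| Missed visit | Window closes | Second letter | Days to Month 6 (Day 180) | Days to Month 12 (Day 360) |
|---|---|---|---|---|
| Week 2 | Day 17 | 17 + 7 = Day 24 | 156 | 336 |
| Month 1 | Day 33 | 33 + 7 = Day 40 | 140 | 320 |
| Month 3 | Day 96 | 96 + 7 = Day 103 | 77 | 257 |
| Month 6 | Day 186 | 186 + 7 = Day 193 | – | 167 |

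Measured to the opening of the MRI windows (Days 174 and 354), each gap is 6 days shorter. With an assumed 2 to 4 weeks of calling first, the gap to Month 6 becomes 142 to 128 days after a missed Week 2 visit (156 − 14, 156 − 28) and 63 to 49 days after a missed Month 3 visit (77 − 14, 77 − 28). At least 167 − 28 = 139 days remain to Month 12 in every case.

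**Effect on the primary analysis.** Protocol 9.3 and SAP section 6 admit a subject to the primary mITT population only with a baseline value and some later value of the parameter. Protocol 6.9 schedules MRI at screening, Month 6 and Month 12. A subject lost before Month 6 with no later MRI therefore has no infarct size after baseline and is out of the primary analysis. SAP section 9 says that maximum likelihood copes with one missing follow-up value but not with both. A subject lost after Month 6 contributes Month 6 only.

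**Effect on power.** I simulated the closed test with the Month 12 means of Protocol Table 4, SD 10, 2:1 allocation and equal strata, using t-tests on Month 12 values and 4,000 runs per setting. Power is above 99% at 100, 93, 82 and 72 completers and about 98% at 62. This agrees with the plan's statement of more than 90% at 100. If the SD were 20 (my assumption), power would be about 72% at 93 completers and 67% at 82, so the small power cost depends on the plan's SD.

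**Weight of one subject.** About 34 placebo and 69 CAP-1002 subjects are planned, with roughly 51/3 = 17 Recent placebo. One loss is 1/34 = 2.9%, 1/69 = 1.4% or 1/17 = 5.9% of the group concerned. These are shares of a group and do not estimate bias.

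**Effect on follow-up time.** Take a subject last seen on Day 30 who misses Month 3, with no later event or medication date. If the recorded termination date (Day 103) becomes the EOS date, SAP 8.9 gives 103 + 1 = 104 days. Observed time is 30 + 1 = 31 days, so 73 days are unobserved.

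**The case against.** The strongest reply is that 7.9 is gentler than it looks. The subject *can* be classed as lost, three calls is a minimum, and anyone who answers a call or the first letter is not terminated. The same section tells staff to attempt the Month 12 testing, to keep in touch at usual visit times if the subject permits, and to phone yearly with consent. All of this stands, so a reader who infers that one missed visit forces a subject out goes further than the text. The safeguards are nevertheless incomplete. They are expressed as what staff should do, an unreachable subject cannot give permission, the yearly calls collect MACE and not MRI, and nothing provides for taking back someone who has been told that participation is over.

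A reader might also infer that SAP 7.6 shuts the database to a terminated subject. It does not. It defines EOS, while SAP 7.7 assigns assessments by study day (Month 6 is Days 136 to 270, Month 12 is Days 271 to 426) without excluding data after EOS. A later MRI in those windows would be usable. The difficulty is that the letter makes one less likely.

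Nor does the plan ignore informative missingness. SAP section 9 specifies multiple imputation for the ITT analysis and a missing-not-at-random sensitivity analysis of the primary endpoint. These are useful, but they are not the primary analysis. The sensitivity imputation is based on subjects who had an ICD inserted during the trial, not on subjects lost to contact.

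Finally, no number of such losses is given, so no bias can be calculated. That is correct.

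**Conclusion.** The point holds as a cheap improvement. Protocol 7.9 permits, without requiring, a termination letter after one missed visit, at least three unanswered calls and seven days' silence. This can happen at about Day 24, 40 or 103, which is 156, 140 or 77 days before the Month 6 MRI. The conditional safeguards soften this but leave no route back.

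The consequence is avoidable and possibly informative missing data in the primary mITT analysis, plus some unobserved time in the safety denominators. It is not a material loss of power under the plan's own means and SD, and the documents do not support the stronger inference that the trial's validity is at risk. The dates rest on the fastest sequence of calls and letter. The follow-up-time example assumes that the recorded termination date is used as the EOS date, which the SAP does not state outright.

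**What to change.** In Protocol 7.9:

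- Record the visit as missed and do not end participation.
- Replace the termination letter with one that leaves the invitation to return open.
- Retry contact at each later scheduled visit, Months 6 and 12 in particular.
- State that the subject may resume visits and MRIs at any time.
- Assign final lost-to-follow-up status only once the Month 12 visit window has passed without contact.

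Which closing day to use is a choice. Protocol 7.3.6 closes the visit at Day 366 and SAP 7.7 closes the analysis window at Day 426; either would serve.

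In SAP 8.9, use the last confirmed contact as the date of last known status for subjects lost to follow-up, instead of a maximum that includes the EOS date. The two changes belong together. If status is held open to Day 366 and 8.9 is left as it is, the subject in the example above would be credited with 366 + 1 = 367 days instead of 31.

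The cost is a few extra contact attempts per site and a small change of SAP wording. Treatment, sample size and the primary model are untouched.

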8 QUALITY CONTROL AND ASSURANCE

Data will be entered using an EDC system. A detailed description of the data collection tools and data management process can be found in the case report form completion guidelines and other data management materials that will be provided to each site. The site must ensure appropriate source data documentation. The Investigator or designee must enter all required subject data in the EDC system in a timely fashion (within 3 weeks of study visit) and an explanation must be documented for any missing data.

A site initiation visit will be conducted at each site participating in the Safety and Randomized Cohorts prior to subject enrollment. During this visit, there will be a review of the study protocol, study procedures, the case report forms, the data collection and submission process, and the site's regulatory obligations as well as any special procedures with the center personnel. A representative from the Sponsor will lead the site initiation visits. All training will be documented. A formal, centralized investigator meeting will be held prior to initiation of enrollment for the Randomized Cohort accompanied by site initiation visits if required/desired by site or Sponsor.

9 PLANNED STATISTICAL METHODS

9.1 General Considerations

The Statistical Analysis Plan (SAP) for the Phase 1 Safety Cohort was drafted prior to the start of Phase 1 enrollment with modifications made in the analysis over time based on requests from DSMB during Phase 1.

Pre-specified analyses will be detailed in a Statistical Analysis Plan (SAP). Descriptive summaries will be provided for all safety and efficacy parameters by cohort (Primary or Exploratory) and stratum (recent or chronic MI). Primary efficacy analyses will be performed for the analysis population using a modified intent-to-treat population with post-baseline outcome data. Handling of missing data will be addressed in the SAP.

All analyses and reports will be developed and validated per Good Clinical Practices. An independent DSMB will monitor the study and make recommendations, if needed, regarding stopping the study due to safety concerns.

